1.0 Study Objectives

The purpose of this study will be to evaluate the clinical efficacy and safety of udenafil, an orally administered, potent and selective inhibitor of phosphodiesterase type 5 (PDE5), versus placebo for the treatment of adolescent subjects who have undergone the Fontan procedure

2.0 Overall Study Design

This study is a randomized, double-blind, 26-week, multicenter trial of udenafil (87.5 mg, twice daily) versus placebo on aerobic exercise performance as measured by change in minute oxygen consumption (VO₂) at maximum exercise effort (maximal VO₂) from baseline to six months in adolescent survivors of the Fontan procedure.

Eligible subjects will be randomly assigned to one of two treatment groups (udenafil or placebo) by a web-based system at the data coordinating center. Randomization will occur within strata defined by ventricular morphology (single left versus single right or mixed).

The first dose of randomized study drug will be administered at the clinic (Visit 1) and outpatient dosing will be used for the remainder of the 26-week study. Subjects will return to the clinic for assessments at 2 weeks (Visit 2), 13 weeks (Visit 3), and 26 weeks (Visit 4) or study completion after initiation of study drug dosing.

Maximal VO₂ will be assessed at Visits 1 and 4 (or study completion) using a braked cycle ergometer following a ramp protocol. Additional assessments will include ventricular performance as measured by echocardiogram, endothelial function assessment with EndoPat®, and serum brain-type natriuretic peptide (BNP) level. Quality of life will be assessed with the Pediatric Quality of Life Inventory (PedsQL), Pediatric Cardiac Quality of Life Inventory (PCQLI), and the Habitual Activity Estimation Scale (HAES).

Blood samples for pharmacokinetic assessments of udenafil and its primary metabolite will be obtained after the first dose of randomized study drug and at Visit 4 (or study completion). Safety will be monitored by adverse event reports, resting vital signs, and clinical laboratory tests.

When an individual subject completes the study, the subject's primary cardiologist will be notified, and the study drug will be stopped; there will be no need to wean subjects off the study drug. Subjects will not be told which drug they received until all recruitment and follow-up is completed per-protocol. All subjects will be invited to participate in an open-label, 12-month safety extension trial of udenafil.

CONFIDENTIAL

The blind for the study will be broken when the later of the following 2 events occur and all database queries have been resolved:

- Visit 4 is completed for the last subject who enters the safety extension trial, or
- The 90-day follow-up is completed for the last subject who does not enter the safety extension trial.

3.0 Sample Size

A sample size of 198 subjects per group will provide 90% power to detect a mean treatment group difference in change from baseline to Week 26 in maximal VO₂ scores of 10%; that is, an improvement of 2.8 mL/kg/min in the udenafil group compared to zero change in the control group, assuming a Type I error of 0.05 and standard deviation of 7.235. A difference of 2.8 represents approximately 0.4 standard deviations, a difference equivalent to a 10% increase from an expected baseline of 28 mL/kg/min.

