9.7.1.4.4 Missing Data

The following imputation method was used for the primary analysis of the primary outcome:

- Subjects who had died or dropped out of the study with unknown vital status were to be assigned a maximal VO₂ of zero at Week 26. No subjects met this criterion.
- Subjects who were known to be alive, but who discontinued from the study (and were missing maximal VO₂ at Week 26) were assigned the latest value available.
- Subjects who completed Week 26, but were physically unable to reach maximum effort in cardiopulmonary exercise testing after 2 attempts, were assigned their baseline value (ie, zero change).

Two additional analyses to assess the impact of missing data were conducted as follows:

- Subjects with missing maximal VO₂ at Visit 4 were assigned a maximal VO₂ of zero.
- Subjects with missing maximal VO₂ at Visit 4 were excluded from analysis (ie, observed cases analysis).

Missing item scores for rating scales were imputed according to published methodology for the scale. Otherwise, missing data were not estimated for secondary efficacy endpoints.

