9.7.2 Determination of Sample Size

A sample size of 198 subjects per group would provide 90% power to detect a mean treatment group difference in change from baseline to Week 26 in maximal VO₂ scores of 10% (ie, an improvement of 2.8 mL/kg/min in the udenafil group compared to zero change in the control group, assuming a Type I error of 0.05 and standard deviation of 7.235). A difference of 2.8, equivalent to a 10% increase from a baseline of 28 mL/kg/min, represents approximately 0.4 standard deviations.

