6.0 Statistics

All statistical tests will be at the 0.05 alpha level, 2-tailed, unless stated otherwise. Probabilities will be rounded to 4 decimal places before assigning statistical significance.

Descriptive statistics for categorical endpoints will include the number and percent of subjects in each treatment group and category. Quantitative endpoints will be summarized for each treatment group with the mean, median, standard deviation, minimum value, and maximum value.

Individual subject data will be presented in data listings, which will include normal reference ranges when appropriate.

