6.4.3 Missing Data

The following imputation method will be used for the primary analysis of the primary outcome:

- Subjects who have died or have dropped out of the study with unknown vital status will be assigned a maximal VO₂ of zero at Visit 4.
- Subjects who are known to be alive, but who discontinued from the study (and are missing maximal VO₂ at Visit 4) will be assigned the latest value available (e.g., value from end of study visit if available, and from baseline visit otherwise).
- Subjects who complete Visit 4, but are physically unable to reach maximum effort in cardiopulmonary exercise testing after two attempts, will be assigned their baseline value (i.e., zero change).

Two additional analyses to assess the impact of missing data will be conducted as follows:

- Subjects with missing maximal VO₂ at Visit 4 will be assigned a maximal VO₂ of zero
- Subjects with missing maximal VO₂ at Visit 4 will be excluded from analysis (i.e., observed cases analysis).

Missing item scores for rating scales will be imputed according to published methodology for the scale. Otherwise, missing data will not be estimated for secondary efficacy endpoints.

CONFIDENTIAL

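### The stated sample-size inputs give about 97% power at 198 per group, not the stated 90%

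*SAP*

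**What the plan says.** SAP 3.0 Sample Size states: "A sample size of 198 subjects per group will provide 90% power to detect a mean treatment group difference". The endpoint is maximal VO₂, taken as the Week 26 value minus baseline. The difference is 2.8 mL/kg/min on udenafil against no change on control, "assuming a Type I error of 0.05 and standard deviation of 7.235". The same paragraph adds: "A difference of 2.8 represents approximately 0.4 standard deviations", and equates 2.8 with a 10% rise from an expected baseline of 28 mL/kg/min.

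SAP 6.0 Statistics fixes the sidedness: "All statistical tests will be at the 0.05 alpha level, 2-tailed, unless stated otherwise".

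The Protocol document, which is a clinical study report, repeats the statement with the same inputs in 9.7.2: "A sample size of 198 subjects per group would provide 90% power to detect a mean treatment group difference". Its section 9.1 gives the target as 400 adolescents, 200 per group.

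Neither sample-size paragraph mentions attrition, dilution of the effect, the imputation rules of SAP 6.4.3, or any other alpha or standard deviation. SAP 8.0 lists the key changes from the protocol, and sample size is not among them.

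**The concern.** A sample-size paragraph should let a reader put its inputs into the standard formula and recover its result. This one gives every input that a two-group comparison of means needs, yet the result is seven percentage points of power away from the one printed. Either an input is missing, or one is misstated, or the power figure is wrong. The documents do not show which.

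What is at stake is reconstruction of the design: a reader cannot tell what, beyond the printed inputs, the trial was sized to allow for. The calculation also had a use during the trial. SAP 6.8 compares a blinded variance estimate at about 200 subjects with the variance used for the sample size, and calls for recalculation and an increase if the estimate is higher. If 198 contains an unstated allowance, that recalculation cannot be done from the SAP text alone.

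**Working it through.** **Inputs.** Difference δ = 2.8, SD σ = 7.235, Type I error 0.05 and n = 198 per group (SAP 3.0); two-sided test (SAP 6.0); equal groups (Protocol document 9.1). Normal quantiles: 1.960 for two-sided 0.05, and 1.2816 for 90% power.

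**Attempt to reproduce 90% at 198 per group.**
- Standard error of the difference: 7.235 × √(2/198) = 0.727.
- Standardised difference: 2.8 / 0.727 = 3.851.
- Power: Φ(3.851 − 1.960) = Φ(1.891) = 0.971. The noncentral t gives 0.970.

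The stated 90% is not reproduced.

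**Size needed for 90%.**
- n = 2 × [(1.960 + 1.2816) × 7.235 / 2.8]² = 140.3, so 141 per group.
- With the t-test, 141 gives 0.8994 and 142 gives 0.9015, so 142 per group.
- 198/142 = 1.39 and 198/141 = 1.40.

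**Rounding does not explain it.** The exact ratio is 2.8/7.235 = 0.387. Using 0.4 widens the gap: n = 2 × (3.2415/0.4)² = 131.3, so 132 (133 with the t-test), and power at 198 is 0.978.

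**Other readings of the same numbers.**

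| Reading | Result |
|---|---|
| One-sided 0.05 | power 0.986 at 198; n = 115 for 90% |
| Two-sided 0.025 | power 0.946 at 198 |
| 198 as the total (99 per group) | power 0.777 |
| Inflation for 10% dropout | 141/0.90 → 157 per group |
| Inflation for 20% dropout | 141/0.80 → 177 per group |
| Dropout needed to turn 141 into 198 | 1 − 141/198 = 28.8% |

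None of these gives 90% at 198 without a large unstated allowance. The baseline covariate in the planned ANCOVA (SAP 6.4.1) would, if anything, raise power.

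**Unstated inputs that would land near 198.** The documents state none of these, and nothing in them favours one over another.
- *Two-sided alpha 0.01:* Φ(3.851 − 2.576) = 0.899; n = 199 for 90%.
- *Dilution of the effect by 15% to 16%:* Φ(0.85 × 3.851 − 1.960) = 0.905 and Φ(0.84 × 3.851 − 1.960) = 0.899.
- *The rule that assigns zero VO₂* (SAP 6.4.3: "Subjects who have died or have dropped out of the study with unknown vital status will be assigned a maximal VO₂ of zero"). Let a share q of each arm have change equal to minus baseline. The arm mean is (1 − q)μ − 28q. The arm variance is (1 − q)(7.235² + μ²) + q(b² + 28²) − mean², with μ = 2.8 or 0 and baseline SD b from 6.1 to 6.9 (Protocol document, Table 13). At q = 2% and b = 6.1 the difference is 0.98 × 2.8 = 2.744 and the variances are 70.64 and 67.41. The standard error is √(138.05/198) = 0.835, and power is Φ(3.286 − 1.960) = 0.908. Over both values of b and both methods, q = 1% gives 0.941 to 0.943, q = 2% gives 0.905 to 0.908, and 90% is reached at q = 2.14% to 2.20%. This assumes equal shares per arm, SD 7.235 among the other subjects and no covariate gain.

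**Link to the variance check.** With δ = 2.8, 198 per group holds 90% power up to σ = 2.8 / [3.2415 × √(2/198)] = 8.59. For a blinded SD between 7.235 and 8.59, SAP 6.8 would call for an increase while the stated formula would still return 198 or fewer.

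**The case against.** The strongest reply is that 198 and 90% may both be right, with only an input left out. The trial protocol (Appendix 16.1.1 of the Protocol document) was not among the documents, and since SAP 8.0 records no sample-size change, the derivation may be there. The imputation rules in SAP 6.4.3 would plausibly have been allowed for at the design stage. Section 9.7.1 of the Protocol document says its statistical methods are summarised from the SAP, so 9.7.2 is a repetition and not a second independent fault. The practical effect is also nil. Section 11.4.2.3 reports that the interim variance required no increase. The SDs of change in Table 13 were 4.056 and 3.672, well below 7.235. The trial is complete, with 400 subjects randomised.

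Much of this stands. It limits the conclusion to a missing or misstated input, and it rules out any claim that the design was too small. It does not remove the mismatch. Several different unstated assumptions come close to 198, so a reader cannot infer which was used. The later report on the rule for death or unknown vital status, "No subjects met this criterion" (Protocol document 9.7.1.4.4), was known only after the trial and says nothing about what was assumed when it was planned.

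**Conclusion.** The concern holds. From the inputs stated in SAP 3.0 and 6.0, power at 198 per group is 97.0% to 97.1%, not 90%, and 90% power needs 141 to 142 per group, not 198. This rests on a two-sided, two-group comparison of means with equal groups and no covariate gain. Confidence is high for the mismatch only; its cause cannot be settled from these documents. The discrepancy is conservative and changes no enrolment, test or result, so it is a documentation fault that should be put right.

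**What to change.** Add a dated note to SAP 3.0 and a matching one to section 9.7.2 of the Protocol document, leaving the planned wording visible. The note should name the input actually used to reach 198 (for example an alpha, a standard deviation, an attrition or dilution allowance, or an assumed share under an imputation rule) and give its value.

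If there was no such input, the note should read: *The stated inputs (difference 2.8, SD 7.235, two-sided alpha 0.05) give about 97% power at 198 per group; 141-142 per group would give 90%.*

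The cost is one note in each document, with no change to enrolment, analysis or results.

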impact of alterations in PVR on exercise capacity for those with other forms of heart disease. Although udenafil may have some effect on maximal VO₂, this effect is blunted by the physiologic ceiling of CVP. The expanded understanding of Fontan physiology in recent years has taught that the assumptions informing the selection of maximal VO₂ as the primary endpoint were inaccurate, and that VO₂ at VAT is a more useful endpoint for this unique cohort of patients.

Overall Efficacy Conclusions

In summary, treatment with udenafil for 26 weeks resulted in improvements in exercise capacity, as well as an improvement in the performance of the single ventricle. Although the primary endpoint did not reach statistical significance, new knowledge of the limits of the Fontan circulation explains why this endpoint is an imperfect choice for this circulation. Even with the limitations associated with maximal VO₂, this endpoint showed a clear trend toward improvement that, coupled with the improvement at the anaerobic threshold, speaks to the efficacy of udenafil to improve exercise capacity in this population. Based on the superior exercise capacity and ventricular performance for udenafil as compared to placebo at Week 26, this study achieved its primary clinical objective for a population with no pharmacotherapeutic options.

12 Safety Evaluation

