6.4 Efficacy Analyses

6.4.1 Primary Efficacy Endpoint (Aerobic Exercise Performance)

The treatment group difference for change in aerobic exercise performance (as measured by VO₂ at maximum exercise effort [maximal VO₂]) from baseline to Visit 4 will be assessed with an analysis of covariance (ANCOVA) with fixed factors for ventricular morphology (single left versus single right or mixed) and treatment group with a continuous covariate of baseline maximal VO₂.

CONFIDENTIAL

Sensitivity analyses will include:

- Primary efficacy analysis performed for the Per Protocol Population
- ANCOVA model to assess treatment group differences in ranked changes of maximal VO₂ for the ITT and Per Protocol Populations.

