6.8 Interim Analyses

A Data Safety Monitoring Board will meet at least twice per year to review safety data. Formal stopping boundaries are not proposed for the 26-week trial. However, the Data Safety Monitoring Board may recommend stopping the study for other reasons, such as safety findings from this trial and other studies, or concerns about study conduct.

In addition, premature termination of this study may occur due to the impact of results released from other studies, due to failure to enroll, or due to withdrawal of study approval by clinical site Institutional Review Boards. In addition, the National Heart, Lung and Blood Institute retains the right to discontinue the study prior to the inclusion of the intended number of subjects, but intends to exercise these rights only for valid scientific or administrative reasons.

After primary outcome data is obtained for approximately half of the originally planned sample size (approximately N=200 subjects) the variance of the primary outcome will be estimated, using a blinded method with lumped variance. If this estimated variance is higher than the one used for the sample size calculations, then the sample size will be recalculated and increased correspondingly. Otherwise, the sample size doesn't change and the trial proceeds as planned. This approach is based on blinded re-estimation of nuisance parameters and doesn't lead to inflation of type I error. It is consistent with the regulatory guidance for industry in adaptive design of clinical trials.

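### The trial was about 1.9 times as precise as its planning SD of 7.235 implies, and its conclusions do not say that the primary 95% CI includes zero and excludes the 2.8 mL/kg/min design difference

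*SAP*

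**What the plan says.** **Planning.** SAP 3.0 states that "A sample size of 198 subjects per group will provide 90% power". The effect it has in view is "an improvement of 2.8 mL/kg/min in the udenafil group compared to zero change in the control group". The SD enters in a separate clause: the figures are obtained "assuming a Type I error of 0.05 and standard deviation of 7.235". SAP 6.0 makes the tests two-sided: "All statistical tests will be at the 0.05 alpha level, 2-tailed, unless stated otherwise". Section 9.7.2 of the protocol document (which is a clinical study report) repeats the calculation, describing 2.8 as 10% above "a baseline of 28 mL/kg/min, represents approximately 0.4 standard deviations". Neither place gives a source for 7.235, says whether it is an SD of level or of change, or allows for dropout.

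**Analysis.** SAP 6.4.1 analyses change from baseline by ANCOVA with factors for ventricular morphology and "treatment group with a continuous covariate of baseline maximal VO₂". SAP 6.4.3 gives a Week 26 value of zero to subjects who died or dropped out with vital status unknown. Report Section 9.7.1.4.4 says nobody met that rule.

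**Interim check.** SAP 6.8 re-estimates the variance blind at about 200 subjects and acts only upward: "If this estimated variance is higher than the one used for the sample size calculations". Report Section 11.4.2.3 says no increase was needed and gives no estimate.

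**Result and conclusion.** Table 13 gives a difference of 0.64 mL/kg/min (SE 0.377, p=0.092), the protocol-specified unit, and 41.04 mL/min (SE 22.709, p=0.071), a unit added after the blind was broken (Section 9.8.2.3). Of maximal VO2, Section 11.4.7 says "this endpoint showed a clear trend toward improvement". Section 13 says that the primary clinical objectives were met.

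**The concern.** The planning paragraph makes 2.8 mL/kg/min look close to the smallest difference that the trial could find reliably. A reader who accepts that may take a non-significant 0.64 as an encouraging but imprecise result, compatible with the effect the trial was built to detect. Whether that is fair depends on the precision actually achieved. If the SD of change was well below 7.235, the interval may rule out the design difference, and a conclusion that speaks only of a trend leaves out the most informative thing the primary analysis shows.

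**Working it through.** **1. The plan's own figure.** Inputs from SAP 3.0 and 6.0: difference 2.8, SD 7.235, two-sided alpha 0.05, 198 per group.

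- Standardised difference: 2.8/7.235 = 0.387, the stated 0.4 after rounding.
- n per group for 90% power = 2 × (1.960 + 1.282)² × (7.235/2.8)² = 2 × 10.51 × 6.68 = 140.3, so 141 (142 by noncentral t).
- At 198 per group, SE = 7.235 × √(2/198) = 0.727 and 2.8/0.727 = 3.85. Power = Φ(3.85 − 1.96) = 97.1% (97.0% by noncentral t).

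The stated 90% is not reproduced. Dropout would have to be 1 − 141/198 = 28.8% to bridge the gap, and none is stated. Two-sided alpha of 0.01 gives 199 per group but contradicts the stated 0.05.

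**2. SD of the analysed change (Table 13, mL/kg/min).**

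- Pooled: √((4.056² + 3.672²)/2) = 3.87.
- Implied by the ANCOVA SE: 0.377/√(2/200) = 3.77.
- 7.235/3.87 = 1.87, a variance ratio of 3.5.
- SE ratio: 0.727/0.377 = 1.93. Against the unadjusted SE of change, 3.87 × √(2/200) = 0.387, it is 1.88.

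With SD 3.87, power for 2.8 at 198 per group is over 99.9%. These SDs use LOCF, which shrinks them slightly: in mL/min the udenafil SD is 238.291 with LOCF and 244.914 for observed cases (Table 12), about 3%.

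**3. What 7.235 might be.**

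- *An SD of level.* The four level SDs in Table 13 run from 6.128 to 6.877. The tables imply a baseline-to-Week-26 correlation of (6.877² + 6.871² − 4.056²)/(2 × 6.877 × 6.871) = 0.83 for udenafil, and likewise 0.84 for placebo. A change SD of 7.235 would need 0.45 and 0.36. But 7.235 exceeds all four level SDs.
- *An SD of change that allows for the zero rule.* Assume that a share p of subjects is assigned zero. Take mean baseline 27.9 with SD 6.51, and mean change −0.56 with SD 3.87 for everyone else. The means are then about 27.4 apart. Variance = p × 6.51² + (1 − p) × 3.87² + p(1 − p) × 27.4². The SD is 5.5 at p = 2%, 6.1 at 3%, 6.7 at 4% and 7.2 at 5%.

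The documents do not decide between these, or exclude a third origin.

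**4. The primary interval.** Estimate ± 1.966 × SE:

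- mL/kg/min: 0.64 ± 0.74 = −0.10 to 1.38. The design difference lies (2.8 − 0.64)/0.377 = 5.7 SE above the estimate.
- mL/min: 41.04 ± 44.65 = −3.6 to 85.7. Ten per cent of mean baseline is 0.10 × (1562.00 + 1626.95)/2 = 159.
- Observed cases in mL/min (Table 12): 44.68 + 1.966 × 23.897 = 91.7, still well below 159.

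Each interval includes zero and excludes 10%.

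**5. The interim check.** The benchmark variance was 3.5 times the final variance of change. Unless the first half of the trial was far more variable than the whole, the upward-only rule could not be triggered. That no increase was needed therefore says little about whether 7.235 was a suitable input.

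**The case against.** The best defence is that this is hindsight. The SAP was final on 23 June 2016, before the first consent on 27 July 2016, and nobody then knew the SD of change. A generous planning SD loses no power, biases nothing and leaves Type I error alone, and a check that can only raise the sample size is a proper safeguard. The zero rule could have justified a large SD, and it happened not to be used. All of that stands, so the SAP should not be rewritten with outcome data.

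It is also true that Table 13 prints the estimate, SE and SDs, so a reader can work out the interval. Section 11.4.7 admits that significance was missed and that the assumptions behind choosing maximal VO2 were inaccurate. That is partial disclosure: it concerns the choice of endpoint and the physiology, and does not tell the reader that the design difference is excluded.

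Four stronger readings are tempting and not supported:

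- *That 7.235 is a between-subject SD of level used by mistake.* It is unlabelled, matches none of the observed level SDs, and could be a change SD under the zero rule.
- *That any mean effect is below 5% of baseline.* This rests on 1.38 against 1.4 in one unit. In mL/min the upper limit is 85.7/1594 = 5.4%. On the log scale (Table 14, mL/kg/min) it is 0.03 + 1.966 × 0.018 = 0.065, or about 7%.
- *That power recomputed afterwards for some smaller effect strengthens the case.* It adds nothing to the interval.
- *That the report blames low power for the missed endpoint.* It does not; it offers a physiological explanation.

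**Conclusion.** The point holds as a fault of reporting and interpretation, not of the test. The stated power does not follow from the printed inputs (97.0%, not 90%). The planning SD is unexplained and nearly twice the SD of change observed. The trial's SE was about 1.9 times smaller than that SD implies; the SAP itself states no precision, so the comparison is with what its inputs imply.

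The consequence is that the primary analysis excludes the 10% improvement used for planning, by a wide margin and in both units, while leaving zero inside the interval. Describing this only as a trend is incomplete. The interval does not show that udenafil has no effect on maximal VO2; smaller effects remain compatible with it.

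This rests on Table 13's LOCF results, on a t multiplier of 1.966, and on reading 10% in mL/min as 10% of the mean baseline of the two groups. That the report never makes the comparison is judged on the text available, from which some pages and figures are absent.

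**What to change.** Change the report only and leave the final SAP as it stands.

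1. **Section 9.7.2.** Give the source of 7.235 and say whether it is an SD of level or of change, or state that the source cannot be recovered. Correct the power from the printed inputs to 97%. Add, marked as known only after the trial, that the observed SD of change was 3.87 mL/kg/min.
2. **Section 11.4.2.3.** Print the blinded interim SD beside 7.235.
3. **Sections 11.4.7 and 13.** In 11.4.7 replace the trend wording for maximal VO2, and in 13 add the same sentence: *difference 0.64 mL/kg/min, 95% CI -0.10 to 1.38; the interval includes zero and excludes the 2.8 mL/kg/min (10%) difference the trial was designed to detect.*

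This needs no new data or patients. The interim SD has to be retrieved from the record of the blinded review. The price is a less favourable reading of the primary endpoint.
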